**Table 4: Dose Modifications for Non-Hematologic Toxicities**

NON-HEMATOLOGIC	Action to be Taken
Renal*	If serum creatinine Grade ≥3 (>3 x baseline or >3 x ULN), hold dose until ≤ grade 2. Monitor serum creatinine at least twice a week until resolution to ≤ grade 2, and then at least one week until it resolves to ≤ grade 1.
Hepatic*	
Transaminitis
 
Grade ≥ 1 Transaminitis (ALT/AST > 1-3 X ULN):
 
 
• Maintain Tenalisib dose and initiate prednisone 40 mg daily.
 
• Monitor AST/ALT weekly until resolved.
 
• Withhold Tenalisib in case of development of grade 2 transaminitis or worsening of Grade 1 transaminitis while on steroids.
 
 
Grade ≥ 3 Transaminitis (ALT/AST >5–20 X ULN):
 
 
• Withhold Tenalisib and monitor ALT/AST twice a weekly until Grade ≤1; restart Tenalisib at 400 mg BID dose level.
 
• Initiate prednisone 1 mg/kg in case no improvement with discontinuation of Tenalisib in 1 week.
 
• Monitor ALT/AST twice a weekly until Grade ≤1; restart Tenalisib at 400 mg BID dose level and taper steroid.
 
• If no immediate response to steroids within 7 days, initiate mycophenolate mofetil.
 
• In case of recurrence of transaminitis at reduced doses, discontinue Tenalisib permanently after assessing risk versus benefit.
 
 
Grade ≥ 4 Transaminitis (ALT/AST >20 X ULN):
 
 
• Tenalisib should be permanently discontinued.
 

	
Bilirubin:
 
 
• Grade <math>\geq 2</math> (<math>> 1.5-3 \times \text{ULN}</math>): Maintain Tenalisib dose. Monitor at least weekly until <math>\leq 1 \times \text{ULN}</math>
 
• Grade <math>\geq 3</math> (<math>> 3-10 \times \text{ULN}</math>): Withhold Tenalisib. Monitor at least weekly until bilirubin is <math>\leq 1 \times \text{ULN}</math>; restart Tenalisib at 400 mg BID dose level.
 
• Grade <math>\geq 4</math> (<math>> 10 \times \text{ULN}</math>): Discontinue Tenalisib permanently
 

Infection	
Grade 3 or higher sepsis or pneumonia
 
 
• Interrupt Tenalisib until infection has resolved.
 

Diarrhea	
Moderate:
 
 
• Maintain Tenalisib dose. Monitor at least weekly until resolved.
 
 
Severe diarrhoea or hospitalization
 
 
• Withhold Tenalisib dose. Monitor at least weekly until resolved.
 
• Restart Tenalisib at 400 mg BID dose level.
 
 
Life threatening diarrhoea
 
 
• Discontinue Tenalisib permanently.
 

Cardiac	
If a QTcF <math>>500</math> msec has been demonstrated, hold dose.
 
The patient will be monitored hourly with ECGs until the QTcF <math><500</math> msec and the QTcF has returned to “<math><30</math> msec from baseline”. Immediate attention to potassium and magnesium and other clinical factors such as oxygenation and ischemia should be addressed.
 
All cardiac events should be treated as per the local standard of care and referral to a specialist if clinically indicated. Any final decisions concerning dose modifications or permanently discontinuing the patient from study drug due to QTcF prolongation will occur after discussion with medical monitor.

OTHER NON-HEMATOLOGIC	Action to be Taken
Grade 3/4 CTCAE	
First occurrence:
 
Hold* dose until toxicity Grade <math>\leq 2</math>; restart Tenalisib at 400 mg BID dose level.
 
Subsequent Occurrences: Hold dose until to <math>\leq</math> Grade 2 or baseline.
 
Discontinue if further dose modification required.

\* If study d\*If the drug is delayed  $>2$  weeks because of an adverse event, treatment strategy should be discussed with medical monitor.

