## **6 TRIAL ASSESSMENT AND PROCEDURE**

### **6.1 Overview**

Schedule of Event (**Table 1**) summarizes the trial procedures to be performed at each visit and is divided into following.

1. Screening (Day -28 day to Day 0)
2. On treatment procedures (C1D1 to C8D28)
3. Treatment beyond Cycle 9 (C9D1 to C26)
4. End of Treatment (Day +7 from last dose)
5. End of Study (Day +30 from last dose)

Individual trial procedures are described in detail below. It may be necessary to perform these procedures at unscheduled time points if deemed clinically necessary by the investigator.

Furthermore, additional evaluations/testing may be deemed necessary by the investigator and or the Sponsor for reasons related to subject safety. In some cases, such evaluation/testing may be potentially sensitive in nature (e.g., HIV, Hepatitis C, etc.), and thus local regulations may require that additional informed consent be obtained from the

[REDACTED]

subject. In these cases, such evaluations/testing will be performed in accordance with those regulations.

Table 1: Schedule of Events for Part 1															
	Screening	Cycle 1		Cycle 2		Cycle 3		C4	C5	C6	C7	C8	C9-26	EOT 	EOS 
Day	D-28 to 0	D1	D15	D1	D15	D1	D15	D1	D1	D1	D1	D1	D1	-	-
Window period	-28	±1	±1	±1	±3	±3	±3	±3	±7	±7	±7	±7	±7	+14	+30
Study Days	D-28 to 0	1	15	29	43	57	71	85	113	141	169	197	-	-	-
Informed Consent 	X	-	-	-	-	-	-	-	-	-	-	-	-	-	-
Demographics 	X	-	-	-	-	-	-	-	-	-	-	-	-	-	-
Medical history 	X	-	-	-	-	-	-	-	-	-	-	-	-	-	-
Vitals 	X	X	X	X	X	X	X	X	X	X	X	X	-	X	-
Height and weight 	X	X	X	X	X	X	X	X	X	X	X	X	-	X	-
Complete Physical exam 	X	-	-	-	-	-	-	-	-	-	-	-	-	X	-
Abbreviated Physical exam 	-	X	X	X	X	X	X	X	X	X	X	X	-	-	-
ECOG Performance Status	X	X	-	-	-	X	-	-	X	X	X	X	-	X	-
Complete blood count 	X	X	X	X	X	X	X	X	X	X	X	X	X 	X	-
Chemistry panel I 	X	X	X	X	X	X	X	X	X	X	X	X	X 	X	-
Chemistry panel II 	X	X	-	-	-	X	-	-	X	-	-	X	-	X	-
Serology 	X	-	-	-	-	-	-	-	-	-	-	-	-	-	-
PT and INR 	X	X	X	X	X	X	X	X	X	X	X	X	-	X	-
Urinalysis (routine)	X	X	X	X	X	X	X	X	X	X	X	X	X 	X	-
Pregnancy test 	X	X	X	X	X	X	X	X	X	X	X	X	-	X	-
12-lead ECGs 	X	X	X	X	X	X	X	X	-	-	-	X	-	X	-
Radiological scan/imaging	X	-	-	-	-	X	-	-	X	-	-	X	X 	X	-

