**Foot notes:**

1. Patient should be re-consented, if informed consent is obtained >30 days prior to the initiation of trial treatment. The first day of Tenalisib administration will be considered as C1D1.
2. Demographic profile will include age, sex and race.
3. Detailed history will be taken at screening that includes history of cancer, past history, number of prior therapies; and prior medication (in last 4 weeks); and other medical history. Any medical significant history at subsequent visit will be captured as adverse event.
4. Vitals will include pulse; blood pressure; respiratory rate and oral temperature that should be done at screening, C1D1 (within 30 minutes prior to dosing) and at the time of clinic visit at all other time points. Supine or sitting position is acceptable depending on the patient condition.
5. Weight will be measured at all visits. Height to be measured at screening only.
6. Physical examination will include lymph node and systemic examination (General Appearance, HEENT, neck, cardiovascular, lungs, abdomen, lymph nodes, genitourinary, extremities, neurological, skin, and musculoskeletal). Complete physical examination will be done at screening visit and EOT. At all other visits, abbreviated examination (directed physical examination) will be done depending on the assessment of tumor.
7. This will include hemoglobin, complete blood count, total leucocyte and differential count and platelet count. Additional investigations will be performed if clinically indicated. Hematology must be done ≤7 days prior to C1D1. However, if these initial examinations are obtained within 72 hours of C1D1; they do not have to be repeated.
8. Chemistry Panel I includes total bilirubin, ALP, AST, ALT, GGT, LDH, sodium, potassium, chloride, calcium, phosphorus, CO2/bicarbonate and magnesium. These tests must be done ≤7 days prior to C1D1. However, if these initial examinations are obtained within 72 hours of C1D1; they do not have to be repeated. These tests will be performed at supplementary visits if clinically indicated.

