9. Chemistry Panel II includes blood glucose, urea/ blood urea nitrogen (BUN), creatinine, albumin, total protein, TSH, T3 (total/free), T4 (free), total Cholesterol, TG, LDL and HDL. These tests must be done ≤7 days prior to C1D1. However, if these initial examinations are obtained within 72 hours of C1D1; they do not have to be repeated. These tests will be performed at supplementary (unscheduled) visits if clinically indicated.
10. Serology includes HIV, HBV and HCV. Historical evidence in the last 4 weeks is acceptable.
11. PT and INR test must be done ≤7 days prior to C1D1. However, if initial examination is obtained within 72 hours of C1D1; this do not have to be repeated. In case of abnormality, additional tests including aPTT to be done as per investigator discretion. This test will be performed at supplementary visits if clinically indicated.
12. This is required for women of child bearing potential. A serum pregnancy test will be performed at screening and C1D1 (within 72 hours) of dosing. Urine pregnancy test will be performed at other visits as indicated.
13. A standard 12-lead ECG will be performed at the defined time points. Additional ECGs will be obtained if clinically indicated. Triplicate ECGs will be performed to confirm significant changes of a single ECG.

14. PET/PET-CT and “diagnostic quality” CT scan will be performed at the time of screening within 28 days of screening. Following screening, CT scans should be repeated at C5D1 and at every 12-Weeks thereafter. PET/PET-CT should be repeated at C3D1 and to confirm CR/PD; and as clinically indicated. Tumor imaging should remain consistent throughout study, and should include those thought by investigator to best capture the status of disease. Baseline scans if already available as SOC within 28-days of screening, is accepted as part of study protocol.
15. Disease response assessment will be performed at C3D1 ( $\pm$  7 days), C5D1 ( $\pm$  7 days) and approximately every 12 weeks thereafter ( $\pm$  7 days), and/ or at the EOT or as clinically indicated (if clinical progression is suspected or for confirmation of complete response/disease progression) using Cheson Criteria 2014.
16. Tenalisisib will be dispensed in a HDPE container having 30 tablets of Tenalisisib.

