**Table 2: Laboratory Tests for Hematology, Chemistry and Urinalysis**

Hematology	Chemistry Panel I	Chemistry Panel II	Urinalysis	Other
Hematocrit	Total bilirubin	Blood glucose	Blood	Serum $\beta$ -hCG
Hemoglobin	Alkaline phosphatase (ALP)	Urea or blood urea nitrogen a	Glucose	Urine pregnancy test
CBC with differentials	Alanine aminotransferase (ALT)	Creatinine	Protein	PT
Platelet count	Aspartate aminotransferase (AST)	Albumin	Specific gravity	INR
WBC (Total and differentials)	Lactate dehydrogenase (LDH)	Total protein	Microscopic exam	
Red blood cell count	Gamma-glutamyl transferase (GGT)	Total Cholesterol		
Absolute neutrophil count	Sodium	Triglyceride (TG)		
Absolute lymphocyte count	Potassium	LDL		

	Calcium	HDL		
	Phosphorous	TSH		
	Carbon Dioxide (CO 2 ) or bicarbonate C	T3 (Total or Free) d		
	Chloride	T4 (free)		
	Magnesium			

a Blood Urea Nitrogen is preferred; if not available Urea may be tested.

b Microscopic exam, if abnormal results are noted.

c One of these tests to be performed depending on standard of care practice followed at the institution.

d Free or total T3 to be performed depending on standard of care practice followed at the institution.

Blood drawn for these tests will be specified in informed consent form (ICF). The investigations will be performed at the local laboratory as decided by the sponsor and investigator. .

Screening laboratory described in **Table 2** will be performed, reviewed, and determined to be acceptable by the site PI/designee after obtaining informed consent and ≤7 calendar days prior to the initiation of treatment. If these initial examinations are obtained within 72 hours (or as otherwise noted) of Cycle 1 Day 1, the investigations need not be repeated. Rescreening can be done at the discretion of PI. The scan and other investigations to document measurable or evaluable disease should be performed ≤28 weeks prior to initiation of treatment.

During screening, active HBV, HCV or HIV infection should be ruled out. To be considered negative for active infection, following algorithm will be used:

- HBV: HBc antibody should be negative or if HBc antibody is positive, HBVDNA should be undetectable
- HCV: HCV antibody should be negative or if HCV antibody is positive, HCVDNA should be undetectable

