#### 7.6.2 Dose modifications

*The dose modification guidelines are intended to be applied when the investigator determines the events related to Tenalisib.*

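### In cycles 1-8 the Grade ≥3 creatinine hold rests on a test scheduled at 3 of 10 visits, with gaps of up to 84 days, although chemistry blood is drawn at all 10

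*Protocol*

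**What the plan says.** The renal row of Protocol Table 4 (section 7.6.2) reads: "If serum creatinine Grade ≥3 (>3 x baseline or >3 x ULN), hold dose until ≤ grade 2". Once a patient has reached that grade, the same row asks for creatinine at least twice weekly until it improves.

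The measurement behind the rule is set by Table 1 and its footnotes. Footnote 9 places creatinine in the second panel: "Chemistry Panel II includes blood glucose, urea/ blood urea nitrogen (BUN), creatinine, albumin, total protein", followed by thyroid and lipid tests. Footnote 8 gives the first panel: "Chemistry Panel I includes total bilirubin, ALP, AST, ALT, GGT, LDH, sodium, potassium, chloride, calcium, phosphorus", then bicarbonate and magnesium, with neither creatinine nor urea. Table 2 ("Laboratory Tests for Hematology, Chemistry and Urinalysis") makes the same split.

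The Table 1 row "Chemistry panel II" is marked at Screening, C1D1, C3D1, C5D1, C8D1 and EOT. The Panel I row is marked at every visit from Screening to C8D1 and at EOT.

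Three provisions bear on how the rule works in practice:

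- Footnote 9 allows extra testing: "These tests will be performed at supplementary (unscheduled) visits if clinically indicated". Section 6.1 says the same of all procedures: "It may be necessary to perform these procedures at unscheduled time points if deemed clinically necessary by the investigator".
- Section 7.6.2 limits the dose rules to drug-related events: "The dose modification guidelines are intended to be applied when the investigator determines the events related to Tenalisib". Section 7.2 makes related the default unless another cause is clear.
- After cycle 8, footnote 19 and section 6.6 require no specific safety laboratory tests of any kind.

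**The concern.** The hold is defined by a laboratory value, so it can operate only when that value is measured. At seven of the ten visits from C1D15 to C8D1 a chemistry sample is taken and no serum marker of renal function is run on it. A patient could meet the protocol's own hold criterion and stay on 800 mg BID until the next Panel II draw.

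The plan treats its other named blood-test triggers differently. Neutrophils, platelets, ALT/AST and bilirubin in Tables 3 and 4 are measured at all ten visits through the blood count and Panel I. The protocol gives no reason for the difference. Section 5.2 also foresees tumor lysis risk by allowing prophylactic allopurinol, yet no creatinine is scheduled between day 1 and day 57.

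At stake is the safety of individual patients during treatment. No efficacy estimate, error rate or sample size is affected.

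**Working it through.** The plan states no figure of its own here, so the check is a count from Table 1.

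**Inputs.** Study days of the visits after C1D1, through C8D1: 15, 29, 43, 57, 71, 85, 113, 141, 169, 197. That is 10 visits. The baseline draw is at C1D1, day 1.

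**Scheduled draws and gaps**, each gap being a draw day minus the preceding draw day:

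| Test | Trigger served | Visits marked, of 10 | Nominal gaps (days) |
|---|---|---|---|
| Panel II | creatinine | 3 (days 57, 113, 197) | 57 − 1 = 56; 113 − 57 = 56; 197 − 113 = 84 |
| Blood count, Panel I | ANC, platelets, ALT/AST, bilirubin | 10 | 14 six times, then 28 four times |
| ECG | QTcF above 500 msec | 7 (days 15, 29, 43, 57, 71, 85, 197) | longest 197 − 85 = 112 |

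**Effect of visit windows.** Table 1 gives ±7 days at C5D1 to C8D1. If windows are anchored to the Table 1 study day, the earliest C5D1 is 113 − 7 = 106 and the latest C8D1 is 197 + 7 = 204. The longest creatinine gap is then 204 − 106 = 98 days.

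**With creatinine in Panel I.** It is measured at 10 of 10 visits. The longest nominal gap becomes 28 days. With windows, C5D1 to C6D1 can reach (141 + 7) − 106 = 42 days.

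**Added assays.** 10 − 3 = 7 per patient. For the 20 Part 1 patients, 7 × 20 = 140 at most, if all reach C8D1.

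**Other analytes on the Panel II schedule.** Table 4 ends with a general row for other non-hematologic Grade 3/4 toxicity, which also requires a hold. Section 7.4.3 has Grade 3 or 4 laboratory abnormalities recorded as adverse events, apart from isolated ones the investigator confirms as not clinically significant. Triglycerides and glucose are in Panel II only, so a related Grade 3/4 rise in either can fall under that row on the same 3-of-10 schedule.

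**The case against.** The strongest reply is that the schedule is a defensible tiering. It tests most often for what has been seen with the drug. Section 1.1.2 reports related Grade ≥3 transaminase elevation and neutropenia and lists no renal event, and section 1.1.1 names thyroid and liver as the target organs. On that evidence triglycerides have the better claim among Panel II analytes, because hypertriglyceridemia is a reported related Grade ≥3 event in study RP6530-1301. This stands, and it is why the point is no more than a suggestion. It does not close the gap for creatinine, which has a dedicated hold row with its own numeric threshold.

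The second reply is that the patient is not unobserved between Panel II draws. Urinalysis, Panel I electrolytes, blood pressure and weight are scheduled at every visit from C1D15 to C8D1, and an abnormality in any of them could justify an unscheduled creatinine under footnote 9. This also stands and narrows the point. None of these measures creatinine, so a rise that produces neither symptoms nor a prompting abnormality is still missed.

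A reader might go further and infer any of the following, which the documents do not support:

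- **That the hold rule cannot be applied.** It can, at the three scheduled draws and whenever testing is indicated.
- **That creatinine is the only neglected trigger.** The ECG schedule and the general Grade 3/4 row show otherwise.
- **That the relatedness condition makes the rule idle.** Section 7.2 defaults to related, so a measured rise would normally count.
- **That the SAP needs a matching edit.** SAP 10.6.3 summarises what the database captured in a closed study, so moving creatinine between columns there changes no result.

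**Conclusion.** The point holds as a low-cost improvement to the protocol as written, for cycles 1-8. Creatinine is scheduled at 3 of 10 visits, with nominal gaps of 56, 56 and 84 days, against 10 of 10 and at most 28 days for the other blood-test triggers named in Tables 3 and 4. The residual exposure is a Grade ≥3 rise with no symptoms and no prompting abnormality. It could go unmeasured for nominally up to 84 days after the last draw, or 98 days if the windows are anchored to the study day. These are upper limits set by the schedule and do not estimate how often or how long a rise would be missed.

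The consequence is modest. The documents give no renal signal, and SAP 5.1 records that the study has closed and that Part 2 will not be performed. A reader might take the gap as evidence of renal harm or of unsafe conduct, but nothing in the documents shows either. The absence of mandated laboratory tests after cycle 8 applies to all analytes and is a separate matter.

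**What to change.** In the protocol, or in any later protocol that reuses this schedule, list creatinine under Chemistry Panel I in Table 1 footnote 8 and in Table 2. Leave the Table 4 threshold and action unchanged, and make no SAP edit. Panel I is also marked at Screening, C1D1 and EOT and carries the same 7-day pre-dose rule, so no existing creatinine draw or eligibility check is lost.

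The laboratory cost is the seven assays per patient computed above, on blood already drawn, with no added visit or venipuncture. More frequent testing will also find some creatinine rises not due to the drug, and these will need follow-up. Panel I is marked for cycles 9-26 subject to footnote 19, which mandates no specific tests, so the change requires no further draw there.

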## 8 ASSESSMENT OF EFFICACY

### 8.1 Specification of the Efficacy Parameters

- **ORR** is defined as sum of CR and PR rates, as assessed by the Investigator according to the Lugano Classification for initial evaluation, staging, and response assessment of Non-Hodgkin lymphoma. Only those patients who have had a pre-treatment baseline efficacy evaluation and at least one post-treatment efficacy evaluation or confirmed disease progression will be considered evaluable for response. Subtype specific and overall ORR will be calculated in Part

1 of the study. Criteria for evaluable subjects for Part 2 will be re-defined based on the results of Part 1.

- **CR** rate will be assessed by the investigator according to the Lugano Classification for initial evaluation, staging, and response assessment of non-Hodgkin lymphoma. For assessment of CR, a post-treatment residual mass of any size is permitted if it is negative on positron emission tomography imaging. Only those patients who have had a pre-treatment baseline efficacy evaluation and at least one post-treatment efficacy evaluation or confirmed disease progression will be considered evaluable for response. Subtype specific and overall CR will be calculated in Part 1 of the study.
- **PFS** is defined as time of the first dose of Tenalisib to disease progression or death. Subjects who die without a reported prior progression will be considered to have progressed on the date of their death. Subjects who did not progress or die will be censored on the date of their last tumor assessment.
- **DoR** is defined as the time when the measurement criteria are first met for PR or CR (whichever is reported first) until the date of documented disease progression or death. For subjects who neither progress nor die, the duration of response will be censored at the date of their last disease assessment.
- **Evaluation of Best Overall Response:** The “best overall response” is the best response recorded from the start of the treatment until disease progression or discontinuation from the study.

#### **Disease parameters:**

- **Measurable disease:** Measurable lesions are defined as those that can be accurately measured in at least two dimensions with conventional techniques (CT/PET/PET-CT, MRI, x-ray) or as >1.5 cm with CT scan. All tumor measurements should be recorded in centimeters.
- **Non-measurable disease (evaluable disease):** All other lesions (or sites of disease) including small lesions, (<1 cm using spiral CT scan) are considered non-measurable disease. Bone lesions, leptomeningeal disease, ascites, pleural/pericardial effusions, lymphangitis, and cystic lesions are all non-measurable.
- **Target lesions:** All measurable lesions up to a maximum of 6 lesions total, representative of all involved organs, should be identified as target lesions and recorded and measured at baseline. Target lesions should be selected on the basis of their size (lesions with the longest SPD diameter), and the highest SUV avidity (high SUV lesions may be prioritized even if not the largest lesions, and their suitability for accurate repeated measurements (either by imaging techniques or clinically). A baseline sum of the diameters (longest for non-nodal lesions, short axis for nodal lesions) for all target lesions will be calculated and reported as the baseline sum

diameters. The baseline sum of the diameters will be used as reference to further characterize any objective tumor regression in the measurable dimension of the disease.

- **Non-target lesions:** All other lesions (or sites of disease) including any measurable lesions over and above the 6 target lesions should be identified as non-target lesions and should also be recorded at baseline. Measurements of these lesions are not required, but the presence, absence, or in rare cases unequivocal progression of each should be noted throughout follow-up.

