**Appendix C: Response Criteria for iNHL- (Cheson et. al. 2014)**

Response and Site	PET-CT–Based Response	CT-Based Response
COMPLETE	Complete metabolic response	Complete radiologic response (all of the following)
Lymph nodes and extra lymphatic sites	Score 1, 2, or 3* with or without a residual mass on 5PS†	Target nodes/nodal masses must regress to ≤ 1.5 cm in LDi
	It is recognized that in Waldeyer's ring or extra-nodal sites with high physiologic uptake or with activation within spleen or marrow (e.g., with chemotherapy or myeloid colony-stimulating factors), uptake may be greater than normal mediastinum and/or liver. In this circumstance, complete metabolic response may be inferred if uptake at sites of initial involvement is no greater than surrounding normal tissue even if the tissue has high physiologic uptake	No extra lymphatic sites of disease
Nonmeasured lesion	Not applicable	Absent
Organ enlargement	Not applicable	Regress to normal
New lesions	None	None
Bone marrow	No evidence of FDG-avid disease in marrow	Normal by morphology; if indeterminate, IHC negative
PARTIAL	Partial metabolic response	Partial remission (all of the following)
Lymph nodes and extra lymphatic sites	Score 4 or 5† with reduced uptake compared with baseline and residual mass(es) of any size	≥ 50% decrease in SPD of up to 6 target measurable nodes and extra-nodal sites
	At interim, these findings suggest responding disease	When a lesion is too small to measure on CT, assign 5 mm × 5 mm as the default value
	At end of treatment, these findings indicate residual disease	When no longer visible, 0 × 0 mm For a node > 5 mm × 5 mm, but smaller than normal, use actual measurement for calculation
Nonmeasured lesions	Not applicable	Absent/normal, regressed, but no increase
Organ enlargement	Not applicable	Spleen must have regressed by > 50% in length beyond normal
New lesions	None	None
Bone marrow	Residual uptake higher than uptake in normal marrow but reduced compared with baseline (diffuse uptake compatible with reactive changes from chemotherapy allowed). If there are persistent focal changes in the marrow in the context of a nodal response, consideration should be given to further evaluation with MRI or biopsy or an interval scan	Not applicable

NO RESPONSE OR STABLE DISEASE	No metabolic response	Stable disease

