\* A score of 3 in many patients indicates a good prognosis with standard treatment, especially if at the time of an interim scan. However, in trials involving PET where de-escalation is investigated, it may be preferable to consider a score of 3 as inadequate responses (to avoid under treatment). Measured dominant lesions: Up to six of the largest dominant nodes, nodal masses, and extranodal lesions selected to be clearly measurable in two diameters. Nodes should preferably be from disparate regions of the body and should include, where applicable, mediastinal and retroperitoneal areas. Non-nodal lesions include those in solid organs (eg, liver, spleen, kidneys, and lungs), GI involvement, cutaneous lesions, or those noted on palpation. Non measured lesions: Any disease not selected as measured, dominant disease and truly assessable disease should be considered not measured. These sites include any nodes, nodal masses, and extranodal sites not selected as dominant or measurable or that do not meet the requirements for measurability but are still considered abnormal, as well as truly assessable disease, which is any site of suspected disease that would be difficult to follow quantitatively with measurement, including pleural effusions, ascites, bone lesions, leptomeningeal disease, abdominal masses, and other lesions that cannot be confirmed and followed by imaging. In Waldeyer's ring or in extranodal sites (eg, GI tract, liver, bone marrow), FDG uptake may be greater than in the mediastinum with complete metabolic response, but should be no higher than surrounding normal physiologic uptake (eg, with marrow activation as a result of chemotherapy or myeloid growth factors).

† PET 5PS: 1, no uptake above background; 2, uptake  $\leq$  mediastinum; 3, uptake  $>$  mediastinum but  $\leq$  liver; 4, uptake moderately  $>$  liver; 5, uptake markedly higher than liver and/or new lesions; X, new areas of uptake unlikely to be related to lymphoma.

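### Protocol Section 8.1 lets avid lesions displace larger ones as targets, contrary to Appendix C, so in patients with more than six measurable lesions the choice can decide whether the size part of CT-based PR is met

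*Protocol*

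**What the plan says.** **Selection in Section 8.1 (Disease parameters).** The cap is six: "All measurable lesions up to a maximum of 6 lesions total, representative of all involved organs, should be identified as target lesions". On which six, the text reads "Target lesions should be selected on the basis of their size (lesions with the longest SPD diameter), and the highest SUV avidity", and a bracketed remark adds that "high SUV lesions may be prioritized even if not the largest lesions". Size comes first, and the SUV priority is optional.

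**Selection in Appendix C.** The footnote defines the measured lesions as "Up to six of the largest dominant nodes, nodal masses, and extranodal lesions selected to be clearly measurable in two diameters", and adds "Nodes should preferably be from disparate regions of the body". SUV plays no part. Section 8.2 refers disease assessment to this appendix.

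**CT-based PR in Appendix C.** Every listed component must be met. For targets it is "≥ 50% decrease in SPD of up to 6 target measurable nodes and extra-nodal sites". For nonmeasured lesions it is "Absent/normal, regressed, but no increase". The footnote counts any lesion not selected as measured as nonmeasured.

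**Non-target lesions in Section 8.1.** They need not be measured. Only whether each is present, absent or has unequivocally progressed is noted.

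**Imaging.** Table 1, footnote 14, schedules CT at C5D1 and every 12 weeks thereafter. PET or PET-CT is done at screening and C3D1, to confirm CR or PD, and as clinically indicated.

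**SAP.** It repeats neither selection rule. Section 10.5.5 summarises best overall response as entered in the CRF.

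**The concern.** Two parts of the protocol give different rules for choosing the lesions on which PR is scored. A lesion chosen for avidity is afterwards judged, on the scheduled CT scans, by size. A larger mass that it displaces becomes a non-target lesion and leaves the SPD altogether.

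ORR is part of the primary objective, and best overall response and DoR depend on the same calls. Response is read by the investigator (Section 8.1), open label (Section 3.4), at local imaging centres (Section 6.4), at about 10 sites (synopsis). Neither document describes a central read or a re-derivation of response from lesion measurements. An optional baseline choice that can differ between sites therefore passes straight into the reported rate.

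**Working it through.** The documents give no figure to reproduce, because Part 1 has no statistical basis for its size (Section 9.2). The check is a reading of the rules followed by an illustration.

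**1. When the choice matters.** With six or fewer measurable lesions, all are targets under Section 8.1 and nothing is displaced. The rules can diverge only with more than six.

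**2. Inputs (lesion sizes assumed, not from the documents).** Six avid nodes of 2 x 2 cm, 4 cm² each, halve to 2 cm² each. One less avid mass of 8 x 6 cm = 48 cm² shrinks to 7.5 x 5.8 cm = 43.5 cm², a fall of 4.5/48 = 9.4%. No new lesions, and no other PR component is failed.

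**3. SPD change under each selection.**
- Avid six: 6 x 4 = 24 to 6 x 2 = 12 cm², so -12/24 = **-50%**. The target component is met.
- Largest six (mass plus five nodes): 48 + 20 = 68 to 43.5 + 10 = 53.5 cm², so -14.5/68 = **-21.3%**. It is not met.

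Under the avid six the mass is nonmeasured. It has regressed slightly, and Appendix C sets no minimum regression, so that component is met as well. The same scans give PR on one selection and SD on the other.

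**4. Other mass sizes.** Keep the 9.4% fall in the mass (m = 0.09375), let its baseline area be B, and let the nodes shrink by a fraction n. The largest-six fall is (mB + 20n)/(B + 20), which reaches 50% when n = [0.5(B + 20) - mB]/20.

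| Mass (cm) | B | Largest-six change, nodes halved | Node shrinkage needed for -50% |
|---|---|---|---|
| 3 x 3 | 9 | -(0.84 + 10)/29 = -37.4% | (14.5 - 0.84)/20 = 68% |
| 5 x 4 | 20 | -(1.875 + 10)/40 = -29.7% | (20 - 1.875)/20 = 91% |
| 8 x 6 | 48 | -(4.5 + 10)/68 = -21.3% | (34 - 4.5)/20 = 148%, impossible |

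The selections disagree for node shrinkage from 50% up to the last column. For the 8 x 6 cm mass they disagree at every shrinkage of 50% or more, so the result does not depend on landing exactly on the threshold.

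**5. Mass strictly unchanged.** The avid six still give -50%, and the largest six give 68 to 58, or -14.7%. PR on the avid six now also depends on the nonmeasured-lesion wording. Read literally, an unchanged mass is neither absent or normal nor regressed, so PR fails. If the absence of an increase is taken as enough, PR stands. The Section 8.1 record cannot settle it: a mass that has shrunk and one that has not are both simply present.

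**6. Direction.** The effect can also run the other way. If the mass fell from 48 to 12 cm² and the nodes did not change, the largest six would go from 68 to 32 (-52.9%) and the avid six would show 0%.

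**7. Effect on ORR.** One patient is 1/20 = 5 percentage points if all 20 are evaluable. For example, 2/20 = 10% (exact 95% CI 1.2% to 31.7%) becomes 3/20 = 15% (3.2% to 37.9%). The step is larger within a subtype.

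**The case against.** Several points on the other side have force.

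- **A reader might infer that a PR can be scored while the main bulk is wholly unchanged.** The documents do not support this as a plain consequence. CT-based PR is conjunctive, and on a literal reading an unchanged nonmeasured mass blocks it. The outcome needs either a lenient reading of that row or slight shrinkage of the mass.
- **A reader might infer that Appendix C demands strictly the six largest lesions.** It does not. It says up to six of the largest dominant lesions, clearly measurable, and its preference for disparate regions can itself admit a smaller lesion. Section 8.1 also puts size first. What remains is that Appendix C gives no priority to avidity and Section 8.1 does.
- **Section 8.1 has no PR threshold of its own.** Its baseline reference is a sum of diameters, which itself differs from the SPD in Appendix C. The illustration joins the Section 8.1 selection to the Appendix C threshold, which is how the two must work together in practice.
- **CT is not the only read.** The C3D1 PET counts towards best overall response, and PET-CT or PET is among the options after cycle 8. This narrows the exposure but leaves the scheduled CT reads from C5D1 affected.
- **Frequency is not shown.** The case needs more than six measurable lesions, a bulky but less avid mass, an investigator who uses the option, and discordant shrinkage. The remark in Section 1.2.1 that most patients present with advanced disease says nothing about lesion counts or SUV patterns in relapsed patients. This stands in full.
- **The study is closed.** The SAP notes under Section 5.1 say that it ended for want of clinically meaningful response and that Part 2 will not be run, and SAP Section 9.1 states no formal hypotheses. This stands too: aligning the text cannot alter that decision.

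**Conclusion.** The two selection rules conflict and should be reconciled. In patients with more than six measurable lesions whose bulk is less avid, the baseline choice alone can decide whether the SPD part of CT-based PR is met: -50% against about -21% in the main illustration, and against -37% to -21% over the mass sizes tried. Those sizes are assumptions. The recording rule for non-target lesions adds to the problem, because it cannot show whether an untargeted mass has regressed, which Appendix C asks for.

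The size of the effect is 5 percentage points of ORR per reclassified patient at 20 evaluable. The documents do not give the number of such patients, so it would be wrong to infer that the reported ORR is in fact inflated, or that the decision against Part 2 is in doubt. What is at stake is the reliability of the reported ORR, best overall response and DoR.

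**What to change.** 1. In Section 8.1, replace the SUV clause with the Appendix C rule: up to six of the largest dominant lesions clearly measurable in two diameters, preferably from disparate regions. Carry the same rule into the imaging instructions.
2. Follow smaller, very avid lesions as non-target lesions and on the PET already scheduled.
3. For each non-target lesion, record at every assessment whether it has regressed, is unchanged or has increased, and state how an unchanged lesion counts towards CT-based PR.
4. For patients already enrolled, where existing baseline scans allow, flag target sets that omit a larger measurable lesion. Report ORR with and without those patients as a sensitivity analysis. The target and non-target listings planned in SAP Section 12 are the starting point.

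**Cost.** One sentence in Section 8.1, one recording item, and no new scans. A small, very avid lesion would no longer be measured as a target. Because non-target lesions need not have been measured, some baseline scans may have to be checked again for the size of omitted lesions. Rewriting Section 8.1 does not change targets already chosen, so for this study the sensitivity analysis is the part with practical effect.
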